### **7.3 Lost to Follow-up**

A patient will be considered lost to follow-up if he or she repeatedly fails to return for scheduled visits (or does not participate in telephone/telemedicine follow-up visits) and is unable to be contacted by the study center.

The following actions must be taken if a patient fails to return to the study center for a required study visit:

- All efforts should be made to ascertain the vital status of the patient.
- The study center must attempt to contact the patient and reschedule the missed visit as soon as possible and counsel the patient on the importance of maintaining the assigned visit schedule and ascertain whether or not the patient wishes to and/or should continue in the study.
- Before a patient is deemed lost to follow-up, the Investigator or designee must make every effort to regain contact with the patient (where possible, three telephone calls and, if necessary, a certified letter to the patient's last known mailing address or local equivalent methods). These contact attempts should be documented in the patient's medical record.
- Should the patient continue to be unreachable, he/she will be considered to have withdrawn from the study. Efforts will be made to collect data from public sources to establish vital status.

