9.1.1. DERIVATIONS

- Time to discontinuation from study (days) = (Date of study discontinuation – Date of Study Day 1 [refer to Section 6.1]) + 1

Date of study discontinuation will be captured on the *Disposition* page of the eCRF.

Patients who are ongoing in the study at the time of an analysis will be censored at the date of the last contact before or on the date of the data cut-off for the analysis and patients who completed the study will be censored at study completion.

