16.2. SECONDARY EFFICACY

16.2.1. SECONDARY EFFICACY ENDPOINTS

16.2.1.1. Incidence of Patients with Oxygen-Free Recovery at Day 29

The first key secondary efficacy endpoint is the incidence of patients with oxygen-free recovery at Day 29, defined as the proportion of patients who were alive, discharged, and not receiving supplemental oxygen at Day 29.

1. The alive status of a patient at Day 29 (yes or no) will be determined as follows based on data captured on the *Death Details* page of the eCRF: patients who died before or on Day 29 will be considered as not being alive at Day 29 while patients without any data captured on this page of the eCRF before or on Day 29 but with some data captured on any other page of the eCRF on or after Day 29 will be considered to be alive at Day 29;
2. The patient’s discharge status (yes or no) at Day 29 will be established as follows based on data collected on the *Ordinal Scale for Clinical Severity* page of the eCRF: a patient will be considered as being discharged at Day 29 if 1) their ordinal scale score is 7 at Day 29 and patient was not discharged to hospice care or 2) their ordinal scale score is 8 at Day 29. Discharge to hospice care status will be verified based on data collected on the *Hospitalization* page of the eCRF. To do so, the outcome of the hospitalization record with the latest stop date before or on Day 29 will be examined. The hospitalization outcome of that record should not be ‘Home: Hospice Care’ or ‘Hospice Medical Facility’ for a patient with an ordinal scale score of 7 at Day 29 to be considered as discharged at that time. Patients who discontinued early from study before Day 29 will be considered as having a missing discharged status at Day 29;
3. The patient’s oxygen-free status (yes or no) at Day 29 will be determined as follows: data collected on the

Supplemental Oxygen and Mechanical Ventilation page of the eCRF will be examined to verify if the patient has a record where the start date of supplemental oxygen/mechanical ventilation is before or on Day 29 and stop date of supplemental oxygen/mechanical ventilation is after Day 29* or is ongoing at Day 29. Patients without such record will be considered as being oxygen-free at Day 29 while patient with such record will be considered as being not oxygen-free at Day 29. Patients who discontinued early from study before Day 29 will be considered as having a missing oxygen-free status at Day 29.

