scale score, while patients with a score of 7 discharged to hospice care will be considered as not having met the event, also regardless of their change from baseline in ordinal scale score. For patients hospitalized and not considered as fit for discharge at Day 29 i.e., patients with an ordinal scale score < 6, the ‘≥ 2-point improvement from baseline’ requirement (yes or no) will be established based on the patient’s change from baseline in the ordinal scale at Day 29, where change from baseline will be computed as defined in Section 6.5.

Refer to Section 16.2.2.1 for handling of missing ≥ 2-point improvement from baseline or fit for discharge on the 8-point ordinal scale for clinical severity status.

16.2.1.3. Incidence of All-Cause Mortality through Day 29

The third key secondary efficacy endpoint is the incidence of all-cause mortality through Day 29, defined as the proportion of patients having died due to any cause before or on Day 29. Patients’ alive/death status by Day 29 will be determined based on data captured on the *Death Details* page of the eCRF. If a patient does not have any data captured on the *Death Details* page of the eCRF by Day 29 but his/her ‘subject status’ captured on the *Contact* page of the eCRF at Day 29 is alive or he/she had some data captured on any other page of the eCRF on or after Day 29, he/she will be considered alive on Day 29.

Refer to Section 16.2.2.1 for handling of missing alive/death through Day 29 status.

[figure not shown]
16.2.1.4. Distribution of Patients across the Categories of the 8-point Ordinal Scale for Clinical Severity at Days 8, 15, and 29

An ‘other secondary efficacy endpoint’ is the distribution of patients across the categories of the 8-point ordinal scale for clinical severity at Days 8, 15, and 29 i.e., the proportion of patients in each category of the 8-point ordinal scale for clinical severity at Days 8, 15, and 29. It is to be noted that patients with a score of 7 discharged to hospice care will be pooled with patients with a score of 1 (death) for this ‘other secondary efficacy endpoint’.

Refer to Section 16.1.1 for the description of the 8-point ordinal scale and to Section 16.2.2.1 for handling of missing ordinal scale scores.

16.2.1.5. Worst Post-Baseline Score on 8-point Ordinal Scale from Baseline to Day 29

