- For the incidence of patients with ≥ 2 -point improvement from baseline or fit for discharge on the ordinal scale at Day 29 (refer to Section 16.2.1.2), the same sensitivity analysis using multiple imputation as described above as for the key secondary efficacy endpoint of incidence of patients with oxygen-free recovery at Day 29 will be performed for this key secondary efficacy endpoint, but using a seed of 1228 ;
- For the incidence of all-cause mortality through Day 29 (refer to Section 16.2.1.3), the same sensitivity analysis using multiple imputation as described above as for the key secondary efficacy endpoint of incidence of patients with oxygen-free recovery at Day 29 will be performed for this key secondary efficacy endpoint, but using a seed of 2007.

• **Sensitivity analysis to missing data assumption #2:**

- For the incidence of all-cause mortality through Day 29, a tipping point analysis will be performed. For patients who discontinued early from the study, all possible combinations of the number of patients

CCI

PPD

Version Number: Amendment 1, v1.0
Version Date: 23Apr2021

CCI

dead or alive at Day 29 will be considered and the main analysis of this key secondary efficacy endpoint will be repeated for each combination.

A dot plot will be produced with number of patients with unknown death status at Day 29 imputed to death for the shared placebo plus SoC treatment arm reported on the x-axis and number of patients with unknown death status at Day 29 imputed to death for the candidate agent plus SoC treatment arm reported on the y-axis, and distinguishing between combination that results in statistically significant treatment effect (a dot is displayed for the combination) vs. not statistically significant treatment effect (no dot is displayed for the combination). The clinical plausibility of the combinations on the boundary will be discussed in the clinical study report (CSR) to evaluate robustness of study conclusions to missing data.

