16.2.5. SUPPLEMENTARY ANALYSES FOR SECONDARY EFFICACY ENDPOINTS

The main analysis of each key secondary efficacy endpoint will be repeated for each subgroup defined in Section 7.7. For subgroups corresponding to one of the factors included in the main model, the corresponding factor will be excluded from the model. For example, the remdesivir use at baseline (yes/no) stratification variable, as captured on the IWRS, will not be included in the analysis of the patients who received remdesivir at randomization subgroup, as captured on the IWRS, and analysis of the patients who did not receive remdesivir at randomization subgroup, as captured on the IWRS.

The following supplementary analyses will also be performed for the incidence to all-cause mortality key secondary efficacy endpoint:

- For the incidence of all-cause mortality through Day 29, the time to all-cause death, in days, will be derived as follows:

- Time to all-cause mortality (days) =

$$(\text{Date of all-cause death/Date of censoring} - \text{Date of Study Day 1 [refer to Section 6.1]}) + 1.$$

The date of death will be taken from data captured on the *Death Details* page of the eCRF.

[figure not shown]
For patients who were alive on Day 29, time to all cause-mortality will be censored at Day 29. For patients with an unknown alive status at the time of the analysis due to missing data, time to all-cause mortality will be censored at the latest date on which the patient was known to be alive before or on the data cut-off date of the analysis. The last date the patient was known to be alive will be the latest date

CCI

PPD

Version Number: Amendment 1, v1.0
Version Date: 23Apr2021

CCI

collected on any page of the eCRF. For patients who discontinued from the study before the time of the analysis, time to all-cause mortality will be censored at the date of study discontinuation, as captured on the *Disposition* page of the eCRF.

Number and percentage of patients with and without the event will be presented by randomized treatment arm. For patients who did not meet the event, the main reason for censoring will be summarized similarly.

The incidence of all-cause mortality through Day 29 along with its two-sided 95% CI by treatment arm will then be estimated using Kaplan-Meier survival curves of the time to all-cause mortality. Kaplan-Meier survival curves by treatment arm will also be provided.

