16.4.5. SUPPLEMENTARY ANALYSES FOR ADDITIONAL EFFICACY ENDPOINT

The time to all-cause death through Day 60, in days, will be derived as follows:

- Time to all-cause mortality through Day 60 (days) =
(Date of death / Date of censoring - Date of Study Day 1 [refer to Section 6.1]) + 1.

The date of death will be taken from data captured on the *Death Details* page of the eCRF.

For patients who were alive or patients with an unknown alive status at the time of the analysis due to missing data, time to all-cause mortality will be censored at the latest date on which the patient was known to be alive before or on Day 60. The last date the patient was known to be alive will be the latest date collected on any page of the eCRF.

For patients who discontinued from the study before Day 60, time to all-cause mortality will be censored at the date of study discontinuation, as captured on the *Disposition* page of the eCRF.

Number and percentage of patients with and without the event will be presented by randomized treatment arm. For patients who did not meet the event, the main reason for censoring (refer to Section 16.1.1) will be summarized similarly.

The incidence of all-cause mortality through Day 60 along with its two-sided 95% CI by treatment arm will then be estimated using Kaplan-Meier survival curves of the time to all-cause mortality through Day 60. Kaplan-Meier survival curves by treatment arm will also be provided.

The 25th percentile, 50th percentile (median), and 75th percentile of time to all-cause mortality (days) with the corresponding two-sided 95% CIs based on the Kaplan-Meier survival curves for each treatment arm will be presented. The estimate of the SEs will be computed using Greenwood's formula, the CI for the median will be calculated according to Brookmeyer and Crowley (1982) and the CIs for the survival function estimates at above mentioned time points will be derived from the Kaplan-Meier estimates using the log-log transformation.

Finally, a Cox proportional hazard model will be performed, including the baseline clinical severity of 2 on the 8-point ordinal scale for clinical severity (yes or no), remdesivir use at baseline (yes or no) stratification variables, both as captured on the IWRS, country (region), and treatment arm as factors. Ties will be handled using the exact method. The hazard ratio of the candidate agent plus SoC vs. placebo plus SoC and its associated two-sided 95% CI will be provided.

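### Any eCRF entry dated on or after Day 29 counts as proof of life, so a patient lost earlier but closed out late can be classed alive and left out of the mortality sensitivity analyses

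*SAP*

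**What the plan says.** **Day 29 status.** Under Master SAP 16.2.1.3, a patient without a Death Details entry by Day 29 is alive if the Contact page says so at Day 29, or if "he/she had some data captured on any other page of the eCRF on or after Day 29, he/she will be considered alive". Section 16.2.1.1 has the same rule for oxygen-free recovery, for patients lacking a death record: those "with some data captured on any other page of the eCRF on or after Day 29 will be considered to be alive at Day 29". Neither section excludes any other page.

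**Close-out.** Disposition is an eCRF page with its own date. Master SAP 9.1.1 says: "Date of study discontinuation will be captured on the" Disposition page. Master Protocol 7.3 asks for contact attempts before a patient is deemed lost ("where possible, three telephone calls and, if necessary, a certified letter"), and then: "Should the patient continue to be unreachable, he/she will be considered to have withdrawn from the study".

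**Sensitivity analyses.** Section 16.2.4 imputes missing status in patients who left the study by Day 29; this is written for oxygen-free recovery and applied to mortality by reference. Its tipping-point paragraph opens with patients who left the study early, without a Day 29 limit. The plot axes then count the "number of patients with unknown death status at Day 29 imputed to death for the candidate agent plus SoC treatment arm", and likewise for placebo.

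**Censoring.** Section 16.2.5 takes the censoring date of leavers from the Disposition page: "For patients who discontinued from the study before the time of the analysis, time to all-cause mortality will be censored at the date of study" (the sentence ends by naming the discontinuation date). Section 16.4.5 (Day 60) censors leavers in the same way and adds, for patients alive or of unknown status: "The last date the patient was known to be alive will be the latest date collected on any page of the eCRF".

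**The concern.** A date on an eCRF page is evidence of life only if someone saw, sampled, dosed or spoke to the patient. A close-out record for a patient who could not be reached shows the opposite: nobody knows. Read literally, the rule turns that absence of information into a status of alive.

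The main mortality analysis already counts unknown status as alive (16.2.2.1). The multiple imputation and the tipping-point analysis exist to test that choice. If the rule relabels some unknown patients as alive before those analyses start, the analyses are run on too few patients and can look more robust than the data allow. In the time-to-death analyses the same dates add event-free time that nobody observed, and more of it in an arm with more loss to follow-up.

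**Working it through.** **1. Can a late close-out arise under the schedule?** Loss to follow-up needs repeated missed visits (Master Protocol 7.3). After discharge the scheduled visits are Day 15, Day 29 (±3) and Day 60. For a patient discharged before Day 15, the second missed visit is Day 29, whose window closes on Day 29 + 3 = Day 32. A close-out after Day 29 is therefore an ordinary course of events. Whether the date entered is the close-out or the last contact is not stated.

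**2. One patient traced through the rules.** Discharged on Day 6, not reached again, Disposition dated Day 35 (assumed to be the close-out date).
- 16.2.1.3: an entry after Day 29 exists, so alive.
- 16.2.4 imputation: status is not missing, and discontinuation is after Day 29, so not imputed.
- 16.2.4 tipping point: included by the opening sentence, excluded by the axis wording.
- 16.2.5: censored at Day 29, as alive on that day, giving 29 − 6 = 23 unobserved event-free days.
- 16.4.5: censored at Day 35, giving 35 − 6 = 29 unobserved days.

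**3. The plan's own mortality figure.** Master SAP 7.1 gives 80% power for 15% against 8.25%, 350 per arm, two-sided 0.05. A normal approximation with difference 0.0675 gives 79.7% (pooled variance) and 80.0% (unpooled). The figure reproduces.

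**4. How many hidden deaths would matter?** Planned deaths are 350 × 0.15 = 52.5 and 350 × 0.0825 = 28.9, so 52 or 53 against 29. Unadjusted Pearson chi-square without correction:

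| Control | Active | Extra active deaths | p |
|---|---|---|---|
| 52 | 29 | 0 | 0.0066 |
| 52 | 34 | 5 | 0.038 |
| 52 | 35 | 6 | 0.0515 |
| 53 | 29 | 0 | 0.0048 |
| 53 | 35 | 6 | 0.040 |
| 53 | 36 | 7 | 0.054 |

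Six or seven of 350 is 1.7% or 2.0% of one arm. An unadjusted logistic Wald test gives p = 0.055 for 53 against 36.

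**5. What the tipping-point grid can show.** The documents give no loss rate; 1% to 5% of the active arm is assumed. Each p is the worst corner: every active-arm patient still unknown dies, no control patient does, starting from 53 against 29.

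| Lost in active arm | All stay unknown | About half classed alive | All classed alive |
|---|---|---|---|
| 4 (1%) | 0.021 | 0.0105 (2 left) | 0.0048 |
| 7 (2%) | 0.054 | 0.015 (3 left) | 0.0048 |
| 10 (3%) | 0.117 | 0.0295 (5 left) | 0.0048 |
| 18 (5%) | 0.517 | 0.092 (9 left) | 0.0048 |

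At 1% nothing tips in any column. At 2% or 3% the conclusion tips only if late close-outs stay in the grid. At 5% it still tips with half of them removed.

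**The case against.** **The patient is not clearly outside the tipping-point analysis.** This stands. The opening sentence covers anyone who left early, and a Day 35 leaver did so before the Day 60 end of study. A reader might infer from the axis labels that such patients are certainly excluded from both sensitivity analyses. The text supports that for the imputation only; for the tipping point, two wordings conflict.

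**The Disposition date may be the last contact.** This also stands. If so, and no other page is dated Day 29 or later, status stays unknown. The documents do not set the convention.

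**There are safeguards.** Protocol 7.3 asks for every effort to establish vital status, including public sources. The schedule asks for Day 29 assessments, where possible, after premature discontinuation. The SAP uses a Contact page status. These reduce the number affected, but the any-page limb requires none of them to have succeeded.

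**The main results do not move.** Largely right. A reader might infer that the mortality estimate itself is biased by this rule. It is not, because unknown status counts as alive anyway. The exception is a hospice-discharged patient, counted dead if unknown after leaving before Day 29 but alive after a late close-out. A reader might also expect the main oxygen-free result to change. It does not: being discharged requires a Day 29 ordinal score, and a missing status counts as a non-event either way.

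**The illustration is a corner case.** Fair. Seven deaths among 18 lost patients is 39%, against planned rates of 8.25% to 15%. One hidden control death also restores significance (53 against 35, p = 0.040). But the SAP intends the study report to discuss the plausibility of boundary combinations, which it cannot do for combinations never plotted.

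**Conclusion.** The concern holds in a limited form. The any-page rule accepts entries that do not show the patient was alive, and can give a wrong Day 29 status. This rests on one convention the documents leave open: that a lost-to-follow-up record, or another administrative entry, carries a date on or after Day 29.

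The consequences are narrow. The imputation omits such patients, the tipping-point paragraph contradicts itself about them, and the survival analyses credit them with unobserved time. The imputation and tipping-point harm concerns COV-01-004 only, since the COV-01-001 and COV-01-005 SAPs drop all sensitivity analyses. The censoring problem reaches further: COV-01-001 keeps the Day 29 mortality Kaplan-Meier analysis, and COV-01-005 keeps those for Day 29 and Day 60.

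Mortality is last in the testing hierarchy, so the issue bears on the credibility of one key secondary result, not on the primary test. The size, six or seven deaths or about 2% of one arm, holds at the planned rates, unadjusted, with no hidden control deaths. How many patients would be affected cannot be derived from the documents. It should be corrected because the rule is wrong as written and the correction is small.

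**What to change.** - **Define one last-known-alive date** from entries that show life: an assessment, sample, dose, hospital stay, successful contact, withdrawal by the patient in person, or traced vital status. Exclude lost-to-follow-up close-out dates, failed contacts and administrative dates. Do not exclude Disposition dates wholesale, since a patient who withdraws in person on Day 35 was alive that day.
- **16.2.1.3:** use this date to class a patient without a death record as alive or unknown at Day 29.
- **16.2.4:** impute and tip all patients with unknown vital status at Day 29, whatever the Disposition date, and bring the opening sentence and axis wording of the tipping-point paragraph into line.
- **16.2.5 and 16.4.5:** censor at this date, capped at Day 29 or Day 60. Carry the change into the survival analyses retained in the COV-01-001 and COV-01-005 SAPs.

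The cost is SAP wording and one derived variable. It should need no new data if the eCRF separates successful from failed contacts, which the documents do not show and should be checked. A few more patients will become unknown, so the sensitivity analyses may look slightly less favourable.

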An ‘other secondary efficacy endpoint’ is the worst post-baseline score (lower scores are worse) through Day 29 in the 8-point ordinal scale (refer to Section 16.1.1), derived from all scores recorded after baseline up to and including Day 29. It is to be noted that patients with a score of 7 discharged to hospice care will be considered as having a

score of 1 (death) instead of a score of 7 for this ‘other secondary efficacy endpoint.

Refer to Section 16.2.2.2 for handling of missing ordinal scale scores.

16.2.1.6. Number of ICU Days from Day 1 through Day 29

An ‘other secondary efficacy endpoint’ is the number of ICU days from Day 1 through Day 29. This endpoint will be considered as an ordinal endpoint.

For each patient, the number of ICU days from Day 1 through Day 29 will be derived based on the sum of the duration of any episodes of ICU admission between Day 1 and Day 29, inclusively, for patients who were alive on Day 29. Episodes of ICU admission will be identified based on data recorded on the *Hospitalization* page of the eCRF, where *Hospitalization Status* is recorded as *ICU/HDU*. For patients who were discharged to hospice care or died before or on Day 29, the number of ICU days from Day 1 through Day 29 will be set to 30 (worst possible scenario).

The duration, in days, of an episode of ICU admission will be derived as follows:

- Duration of an episode of ICU admission (days) = (Date of ICU discharge – Date of ICU admission) + 1

[figure not shown]
If the start date of an episode of ICU admission is prior to Day 1, it will be set to the date of Study Day 1 (refer to Section 6.1) when deriving ICU duration for that episode.

If an episode of ICU admission is ongoing at Day 29 or at the time of analysis, the stop date of the admission will be set to the minimum of:

- The start date of any subsequent ICU admission;
- Day 29;
- The data cut-off date for the analysis.

If there are any overlapping dates of ICU admission, a Day will only be counted once when deriving the overall number of ICU days for a patient. For example, if a patient has a record where the start and stop Study Days of the ICU/HDU admission are Day 3 and Day 10, respectively, and another record where the start and stop Study Days of ICU/HDU admission are Day 9 and Day 12, respectively, Days 9 and 10 will be counted only once in the overall number of ICU days for that patient.

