Refer to Section 16.2.2.2 for handling of missing number of ICU days from Day 1 through Day 29.

16.2.1.7. Number of Invasive Mechanical Ventilator Days from Day 1 through Day 29

For each patient, the ‘other secondary efficacy endpoint’ of the number of invasive mechanical ventilator days from Day 1 through Day 29, inclusively, will be considered as an ordinal endpoint and derived similarly to the number of ICU days from Day 1 through Day 29 (refer to Section 16.2.1.6) but using the data collected on the *Supplemental Oxygen and Mechanical Ventilation* page of the eCRF where *Type of supplemental oxygen* is recorded as *Invasive Mechanical Ventilation*.

Refer to Section 16.2.2.2 for handling of missing number of invasive mechanical ventilation days from Day 1 through Day 29.

16.2.1.8. Incidence of Patients with Clinical Recovery by Days 8, 15, and 29

[figure not shown]
An ‘other secondary efficacy endpoint’ is the incidence of patients with clinical recovery at Days 8, 15, and 29, defined as the proportion of patients being fit for discharge (i.e., patients achieving a score of 6, 7, or 8 on the 8-point ordinal scale for clinical severity; refer to Section 16.1.1) at Days 8, 15, and 29, respectively, as per data recorded on the *Ordinal Scale for Clinical Severity* page of the eCRF. It is to be noted that patients with a score of 7 discharged to hospice care will not be considered as being fit for discharge for this ‘other secondary efficacy endpoint’.

Refer to Section 16.2.2.1 for handling of missing clinical recovery status by Days 8, 15, and 29.

16.2.1.9. Incidence of Patients with Sustained Clinical Recovery as Confirmed by Day 60 Follow-up

An ‘other secondary efficacy endpoint’ is the incidence of patients with sustained clinical recovery as confirmed by Day 60 follow-up, defined as the proportion of patients considered as being fit for discharge (i.e., achieving a score of 6, 7, or 8 on the 8-point ordinal scale for clinical severity) through Day 29, without re-hospitalization by Day 60 (refer to Section 16.1.1), as per the *Ordinal Scale for Clinical Severity* and *Hospitalization* pages of the eCRF. It is to be noted that patients with a score of 7 discharged to hospice care before or on Day 29 will not be considered as being fit for discharge for this ‘other secondary efficacy endpoint’.

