16.2.2. MISSING DATA IMPUTATION METHOD FOR SECONDARY EFFICACY ENDPOINTS

16.2.2.1. Binary Endpoints

For the *incidence of oxygen-free recovery at Day 29* endpoint, the algorithm defined in Section 16.2.1.1 will first be applied. Then, patients with a missing oxygen-free recovery status at Day 29 will be considered as not having met the event for this key secondary efficacy endpoint.

For the *incidence of patients with ≥ 2-point improvement from baseline or fit for discharge on the ordinal scale at Day 29* endpoint (refer to Section 16.2.1.2), patients with a missing ordinal scale score at Day 29 due to patient’s death, discontinuation from study before or on Day 29 or for any other reason (with the following exception) will be considered as not having met the event at Day 29 for that key secondary endpoint. The only exception is for patients with a missing ordinal scale score at Day 29 for which the latest non-missing ordinal scale score before Day 29 was 7 (but not discharge to hospice care) or 8. These patients will be assumed to be fit for discharge at Day 29 and so, as having met the event.

For the *incidence of all-cause mortality through Day 29* endpoint (refer to Section 16.2.1.3), patients with an unknown alive/death status at Day 29 due to discontinuation from study for a reason other than death or missing data will be considered as alive in the analysis, exception of patients for who the last-missing ordinal scale score was 7 and that have been discharged to hospice care before discontinuing from study before Day 29. These patients will be considered as dead at Day 29 for the main analysis of this key secondary efficacy endpoint.

[figure not shown]
For the *clinical recovery by Day 8* endpoint (refer to Section 16.2.1.8), any patient who died before or on Day 8, discontinued from study before or on Day 8 or with missing clinical recovery status at Day 8 will be considered as not having clinical recovery by Day 8. Missing *clinical recovery by Days 15 and 29* will be handled similarly.

For the *sustained clinical recovery as confirmed by Day 60* follow-up endpoint (refer to Section 16.2.1.9), any patient who died before or on Day 60, discontinued study before Day 60 or with a missing 8-point ordinal scale score at Day 60 will be counted as not having sustained clinical recovery.

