16.2.2.2. Ordinal Endpoints

Missing *ordinal scale scores* will be imputed as follows for the distribution of patients across the categories of the 8-point ordinal scale for clinical severity at Day 8 endpoints (refer to Section 16.2.1.4):

CCI			
PPD		Version Number:	Amendment 1, v1.0
		Version Date:	23Apr2021
CCI			

- Patients who died prior to Day 8 will have a score of 1 used for Day 8;
- For all other occurrences of patient with missing ordinal score at Day 8 (e.g., patients who discontinued from the study before Day 8, etc.), the last non-missing post-baseline ordinal scale score before Day 8 (included data collected at unscheduled post-baseline visits) will be used to impute the missing ordinal scale score at Day 8 exception of patients for who the last non-missing post-baseline ordinal scale score before Day 8 is 7 that were discharged to hospice care. For these patients, the missing ordinal scale score at Day 8 will be imputed to 1.

Missing ordinal scale score at Days 15 and 29 will be imputed similarly.

For the *worst post-baseline score on the 8-point ordinal scale from baseline to Day 29* endpoint (refer to Section 16.2.1.5), patients who have died prior to Day 29 will have their worst post-baseline ordinal scale score from Day 1 to Day 29 set to a score of 1. For patients who are alive at Day 29, no imputation of missing post-baseline ordinal scale scores will be performed. The worst post-baseline ordinal scale score will be identifying among the non-missing post-baseline ordinal scale scores (including data collected at unscheduled post-baseline visits).

For the *number of ICU days and number of invasive mechanical ventilation days* endpoints (refer to Sections 16.2.1.6 and 16.2.1.7, respectively), missing data will not be imputed.

[figure not shown]

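### ICU-day and ventilator-day counts have no rule for patients who leave before Day 29, and the open-episode rule read literally credits some of them with unobserved days

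*SAP*

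**What the plan says.** Master SAP 16.2.1.6 computes the count by adding up the length of "any episodes of ICU admission between Day 1 and Day 29, inclusively, for patients who were alive on Day 29". Patients who die or go to hospice care by Day 29 are given 30.

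For stays without an end, the rule starts "If an episode of ICU admission is ongoing at Day 29 or at the time of analysis, the stop date of the admission" and sets that date to the earliest of three: the start of a later ICU admission, Day 29, and the third item, "The data cut-off date for the analysis". The date of leaving the study is not among them.

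Ventilator days (16.2.1.7) are "derived similarly to the number of ICU days from Day 1 through Day 29", from a different eCRF page.

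The SAP expects that a count can be missing: "Refer to Section 16.2.2.2 for handling of missing number of ICU days from Day 1 through Day 29". Section 16.2.2.2 then says of both counts that "missing data will not be imputed". No section says when a count is missing.

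Under 16.2.3.2 both counts go into a proportional odds model. Under 7.4 and 16.2.3, non-key secondary endpoints receive nominal p-values only.

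**The concern.** Other endpoints in the same SAP say what to do with leavers. The primary endpoint censors them at discontinuation (16.1.1), oxygen-free recovery first gives them a missing status (16.2.1.1), and the supplementary time-to-death analysis censors them at discontinuation (16.2.5). The two day counts have no such line, so the general summing rule has to serve.

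That rule uses a patient's last recorded location to determine the unobserved days. A leaver last seen in ICU can be placed next to the death value, and a leaver last seen on the ward can receive the best possible value. If these scores enter the model as observed data, part of the comparison rests on days nobody saw. Two programmers could also build different datasets from the same text.

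**Working it through.** **Inputs**, all from Master SAP 16.2.1.6 unless stated:
- Episode length = stop date − start date + 1. Starts before Day 1 are moved to Day 1, and overlapping days count once.
- Open episode: stop = min(next ICU start, Day 29, data cut-off).
- Death or hospice discharge by Day 29: 30.
- Assumed for the examples: the data cut-off falls after the patient's Day 29, there is no later ICU admission, and the site leaves the ICU record open when the patient leaves.

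**The plan's own figures.** The longest count for a survivor is 29 − 1 + 1 = 29, so 30 is one step above the maximum, as intended. The SAP's overlap example (Days 3–10 and Days 9–12) gives 8 + 4 − 2 = 10 distinct days, with Days 9 and 10 counted once.

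**Open ICU record at leaving, patient classed as alive on Day 29**
- ICU from Day 1, leaves on Day 3. Literal rule: 29 − 1 + 1 = 29. Observed: 3 − 1 + 1 = 3. Unobserved days credited: 29 − 3 = 26. The score is one rank from the death value.
- ICU from Day 3, leaves on Day 10. Literal rule: 29 − 3 + 1 = 27. Observed: 10 − 3 + 1 = 8. Unobserved days credited: 27 − 8 = 19.
- ICU from Day 3, leaves on Day 4, 20 or 28. The literal count is 27 each time, against 2, 18 and 26 observed. The literal count does not depend on when the patient left.

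**No ICU record at leaving, patient classed as alive on Day 29.** There is nothing to sum, so the count is 0. For a patient leaving on Day 3, 29 − 3 = 26 days are again unobserved.

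**Can a leaver be classed as alive on Day 29?** Section 16.2.1.6 does not say how this is set. Section 16.2.1.3 accepts a Contact page status of alive at Day 29, or any eCRF data on or after Day 29. Master Protocol 7.3 has vital status sought from public sources after loss to follow-up. A leaver can therefore be known to be alive at Day 29 with no ICU or ventilator data after leaving.

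**Which analyses use the counts.** The COV-01-001 and COV-01-005 SAPs (Section 16 and 16.2.3.2) only summarize them. The COV-01-004 SAP (Section 16) keeps the Master SAP analysis, so the model comparison applies there only.

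**How many patients.** The documents give no leaver rate. If 2% to 10% of about 700 patients (350 per arm) left before Day 29, that is 14 to 70 leavers. The number scored wrongly would be smaller, because it needs the alive classification and the absence of later data.

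**The case against.** The strongest reply is that the SAP contains no instruction to fill in leavers. Summing is limited to patients alive on Day 29. A leaver with unknown status fits neither that branch nor the death and hospice branch, and the reference to 16.2.2.2 shows that missing counts were expected. Read together, these passages are consistent for that group. This stands.

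A reader might go further and infer that the SAP fills in every leaver and so contradicts its own no-imputation rule, citing 16.2.2.1, where patients with unknown status "will be considered as alive in the analysis". The documents do not support that: the sentence is written for the all-cause mortality endpoint, and nothing extends it to the day counts. Nor is a value of zero for ward leavers written anywhere; it follows only from summing an empty list.

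Two more limits stand. The open-episode result needs the site to leave the record open; if a stop date is entered, the rule does not apply. The eCRF completion guidelines are not among the documents. Also, stopping treatment is not leaving the study (Master Protocol 7.1), and Day 29 assessments are attempted for early leavers (Master Protocol 1.3, footnote a), so 26 unobserved days out of 29 is an extreme case.

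What the reply does not remove is the leaver documented as alive at Day 29 with an open record and no later data. For that patient the stop-date list yields a definite count that includes unobserved days.

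**Conclusion.** The point holds as a missing leaver rule whose literal workaround gives wrong values in a defined group. For a leaver classed as alive on Day 29 with an open ICU or ventilator record, unobserved days are credited up to Day 29, at worst 26 or so in the examples shown. For a leaver classed as alive with no record, the sum is 0. Both sit badly with the no-imputation statement in 16.2.2.2. For leavers of unknown vital status the text is ambiguous and may already mean missing.

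The stakes are small. These are two non-key secondary endpoints with nominal p-values, the model comparison applies to COV-01-004 only, and the primary and key secondary tests are unaffected. The direction of any bias is not fixed, because it depends on where patients were when they left. The conclusion assumes that some records stay open at leaving and that some leavers are known to be alive at Day 29; the documents quantify neither. It is a minor point, worth settling before programming.

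**What to change.** In Master SAP 16.2.1.6 and 16.2.1.7, state that:
- a patient who discontinues before Day 29 without death, hospice discharge or documented ICU (or ventilator) status through Day 29 has a missing value, handled under 16.2.2.2;
- the open-episode rule applies only to patients documented as still in ICU (or on the ventilator) at Day 29 or at the data cut-off;
- death and hospice discharge keep the value 30.

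Do not add the discontinuation date to the stop-date list. Once undocumented leavers are missing, the cap is redundant for them. For a leaver whose stay is documented beyond the leaving date, it would cut off days that are known.

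The cost is two sentences per section. The downside is that a few patients drop out of these two non-key secondary analyses.
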